5.2.1. Abaloparatide-sMTS

Abaloparatide-sMTS is a drug device combination product consisting of the drug (abaloparatide: $ZnCl_2$ in 1:2:2 molar ratio, HCl < 0.1%) coated onto the sMTS array and contained within the following packaging system:

- The primary packaging components with delivery functions include:
 - An array patch for adhering the drug formulation-coated sMTS array to the skin
 - A tray that holds and protects the coated array patch and inserts it into an applicator
- The primary packaging components with protective functions include:
 - A pod that holds the insert
 - A lid heat sealed to the edges of the pod

- The secondary packaging includes:
 - A desiccant
 - A foil patch, heat sealed, that contains the sealed pod and desiccant

The applicator is a spring-powered device that, when pressed against the skin of the thigh, inserts the drug formulation-coated sMTS array tips into the dermis at a predetermined force. In contrast to traditional transdermal delivery systems, the sMTS array penetrates the stratum corneum to deliver the drug formulation following a short wear time (ie, 5-minutes).

5.2.2. Abaloparatide-SC

Abaloparatide-SC is supplied in a single-patient-use prefilled pen that delivers 80 μg of abaloparatide as an SC injection into the periumbilical region of the abdomen and is marketed in the US as TYMLOS[®].

5.3. Packaging, Labeling, and Storage

5.3.1. Packaging and Labeling

Abaloparatide-sMTS arrays and abaloparatide-SC cartridges will be supplied separately to the study site by the Sponsor. Abaloparatide-sMTS applicators for transdermal application and abaloparatide pens for SC injection will also be supplied. All packaging operations will be performed in accordance with Good Manufacturing Practices.

Calcium and vitamin D supplements will be provided as packaged by the manufacturer and will not be relabeled for the study.

All study drug will be labeled with a caution statement and other information required by local Regulatory Authorities.

5.3.2. Storage

Calcium and vitamin D supplements should be stored according to the manufacturer recommendations on the bottle.

5.3.2.1. Abaloparatide-sMTS

Prior to study drug being dispensed to a subject, abaloparatide-sMTS must be kept in a secure, limited-access storage area at 2° to 8°C (36° to 46°F).

Subjects should remove abaloparatide-sMTS from refrigerated storage approximately 1 hour prior to administration. Abaloparatide-sMTS patches used during the study site visits will be carefully placed in a supplied container using minimal manipulation and will be frozen for returning to the manufacturer for further inspection and analysis together with residual drug swabs. Refer to the Pharmacy Manual for additional details.

5.3.2.2. Abaloparatide-SC

Prior to study drug being dispensed to a subject, abaloparatide-SC must be kept in a secure, limited-access storage area at 2° to 8°C (36° to 46°F).

After the abaloparatide-SC injection pen is used for the first time, the pen may be stored for 30 days at room temperature, 20°C to 25°C (68°F to 77°F). Unused pens should be refrigerated until initial use. Additional instructions will be provided to sites in the Pharmacy Manual.

5.4. Study Drug Administration

Subjects will be encouraged to drink 8 ounces of water 1 to 2 hours prior to dosing.

5.4.1. Abaloparatide-sMTS

Prior to the administration of abaloparatide-sMTS, the application site will be prepped, cleaned with an alcohol wipe, left to air dry for a couple of minutes, and examined in order to assure that the area is not compromised.

[figure not shown]
Before loading the abaloparatide-sMTS into the patch holder of the applicator, the subjects should check the abaloparatide-sMTS patch for any damages. If damaged, the abaloparatide-sMTS patch should be replaced with a new one. In addition, subjects should also be instructed to place the damaged abaloparatide-sMTS in a container that was provided and to bring this together with any used and unused patches at the next site visit. Please refer to the Pharmacy Manual for further details.

5.4.2. Abaloparatide-SC

Before use of abaloparatide-SC, subjects will perform a priming procedure after loading a new cartridge into the pen. Instructions for this procedure will be provided in a Pharmacy Manual. The contents of the medication cartridge will be inspected before each injection. If the cartridge contents are not clear and not colorless or if the cartridge contains visible particles, that cartridge will not be used and a new cartridge will be chosen.

5.5. Treatment Assignment

All subjects who sign informed consent for the study will be assigned a unique 6-digit subject ID which will be used to identify subjects throughout the study and on the eCRFs.

Subjects who met the study's eligibility criteria and have successfully completed the Screening and Pretreatment Periods, will be assigned sequentially to a randomized treatment group on Day 1 of the Treatment Period. Subjects will only receive 1 subject ID at the time of screening and therefore, will not receive a new identifier at randomization.

Prior to study start, the Sponsor's statistician will be responsible for overseeing the preparation of the master randomization scheme that will be used to package study drug into kits and for the Interactive Response Technology (IRT).

5.6. Dosing and Administration

On Day 1, subjects will be trained by study personnel how to self-administer study drug with the abaloparatide-SC injection pen or the abaloparatide-sMTS applicator. If a subject requires assistance with study drug administration, an individual (eg, primary caregiver) who has been trained by study personnel may provide such assistance. Subjects are to be instructed to self-administer at home in a location where they have the ability to sit or lie down.

Subjects will self-administer a single daily dose of 80 µg of abaloparatide-SC or 300 µg of abaloparatide-sMTS during the Treatment Period beginning on Day 1 and until Month 12 or the EOT visit.

The first self-administration of abaloparatide-sMTS or abaloparatide-SC will occur at the study site on Day 1 under observation. On the days of study site visits, study drug **must be administered at the study site** to accommodate pre-administration and post-administration procedures.

The subject should self-administer study drug while in a sitting or lying position. The subject should remain in that position for approximately 5 minutes.

At any visit during which study drug is administered, the subject is to remain under observation for a minimum of 60 minutes. When scheduled (see Table 1), an orthostatic blood pressure measurement will be taken 60 minutes after administration. On the days when blood sampling is required after study drug administration, the subject is to remain in the vicinity of the study site for the blood collections scheduled up to 4 hours after study drug administration.

Subjects will also be provided with written instructions on how to use abaloparatide-SC and abaloparatide-sMTS. Study drug should be administered at approximately the same time each day; morning administration is suggested. If a dose is missed, the dose should be administered as soon as possible up to 12 hours after the missed dose schedule. Anytime thereafter, the dose should be skipped and study drug should be administered at the next scheduled time on the following day.

All abaloparatide-SC doses are to be given in the periumbilical region, rotating the site of injection each day. All abaloparatide-sMTS doses are to be applied on the thigh for 5 minutes. If it is deemed medically necessary for the study drug to be administered at an anatomic site other than what is required per protocol, the alternate site of study drug application/injection is to be recorded and the reason for change documented in the medical chart in the source documents as a protocol deviation.

Subjects will be dispensed abaloparatide-SC pens each month and will be instructed to use a new abaloparatide-SC injection pen after each 30-day period. A new set of abaloparatide-sMTS patches will be provided after each 30-day period. At each study site visit during the Treatment Period, the used and unused abaloparatide-SC injection pens and sMTS patches should be returned. All returned study drug should either be destroyed at the study site following that site's local procedures or sent to a depot identified by the Sponsor.

5.7. Treatment Compliance

To ensure treatment compliance, the Investigator or designee will supervise all study drug administration that occurs at the site. At each study visit, the Investigator or designee will review subject compliance with study drug administration and remind the subject of study drug dosing requirements.

For abaloparatide-SC, subject compliance will be ascertained by using the data entered on the subject diaries and the measurement of residual volume of study drug in the cartridge.

Similarly, subject compliance for abaloparatide-sMTS will be ascertained by using the data entered on the subject diaries and total used and unused patches returned at each study visit.

Discrepancies will be discussed with subjects, documented in the medical charts, and recorded in the eCRF as appropriate. If a subject does not take all study drug (abaloparatide-SC or abaloparatide-sMTS) and calcium and vitamin D supplements as prescribed, the reason for the missed dosing is to be recorded by the subject in their diary.

If a subject demonstrates continued noncompliance of study drug dosing despite educational efforts, the Investigator should contact the Sponsor's medical monitor to discuss possible discontinuation of the subject from the study.

5.8. Drug Accountability

The Investigator or designated site staff will maintain records documenting the dates and amounts of the following:

- Abaloparatide-sMTS patches/abaloparatide-SC pens received
- Abaloparatide-sMTS patches/abaloparatide-SC pens dispensed to the subjects
- Abaloparatide-sMTS patches/abaloparatide-SC pens returned by the subjects
- Abaloparatide-sMTS patches/abaloparatide-SC pens returned to Sponsor/designee or destroyed at the site

Subjects will be instructed to return all used and unused study drug to the site. The study drug will be retained at the site until inventoried by the study monitor and approved for destruction or return. The study monitor will verify study drug records and inventory throughout the study.

6. STUDY PROCEDURES AND SCHEDULE

6.1. Study Procedures

6.1.1. Study-Specific Procedures

Study-specific assessments are detailed in this section and outlined in Table 1. At Screening, any safety laboratory results falling outside of the reference ranges may be repeated 1 time at the discretion of the Investigator.

6.2. Study Schedule

Study assessments are to be performed according to the Schedule of Events (Table 1). There is a \pm 4-day window for each study site visit.

The study will consist of a Screening Period (up to 2 months), a Pretreatment Period (1 week), a Treatment Period (12 months), and a post treatment Follow-Up Period (1 month). For the purpose of this study, 1 month is equal to 30 days.

During the Treatment Period, subjects will self-administer study drug once a day for 12 months and visit the study site as follows:

- Study drug administration, study procedures, and assessments: Day 1, Day 14, Month 1, Month 3, Month 6, Month 9, and Month 12
- Study drug administration and assessments: Month 2, Month 4, Month 5, Month 7, Month 8, Month 10, and Month 11

6.2.1. Schedule of Assessments and Procedures

A comprehensive Schedule of Assessments and Procedures is presented in Table 1.

Table 1: Schedule of Assessments and Procedures

Visit		1	2	3	4	5	6	7	8	9	10	11	12	13	14	15	16	17
Study Da Month Procedure (Mo.): Visit Window (Days)	So	creen N/A	Pre-TX N/A	Day 1 ± 4	Day 14 ± 4	Mo. 1 ± 4	Mo. 2 ± 4	Mo. 3 ± 4	Mo. 4 ± 4	Mo. 5 ± 4	Mo. 6 ± 4	Mo. 7 ± 4	Mo. 8 ± 4	Mo. 9 ± 4	Mo. 10 ± 4	Mo. 11 ± 4	Mo. 12/ EOT ± 4	Follow -up/ EOS ²¹ ± 4
Duration		Up to 2 mo.	1 week	N/A	N/A	N/A	N/A	N/A	N/A	N/A	N/A	N/A	N/A	N/A	N/A	N/A	N/A	N/A
Informed consent		X																
Verification of entry criteria		X	X															
Physical examination ¹		X																
Review of medical histo	ry ²	X																
Symptom-directed physic examination	cal		X	X		X		X			X			X			X	X
Vital signs ³		X	X	X		X		X			X			X			X	X
Weight measurement		X		X		X					X						X	
Height measurement ⁴		X	X	X		X		X			X			X			X	X
Electrocardiogram ⁵		X		X													X	X
Urinalysis (dipstick) ⁶		X		X		X					X						X	
Chemistry blood collection ⁷		X		X		X					X						X	
Hematology blood collection ⁷		X		X		X					X						X	
Coagulation (PT and PT blood collection ⁷	T)	X															X	
PTH(1–84) ⁷		X															X	
25-hydroxyvitamin D level ⁷		X															X	
1,25-dihydroxyvitamin I level)			X													X	
Estradiol, FSH		X																
Thyroid stimulating hormone ⁸		X																
Study drug assignment v IRT				X														
Subject training for studdrug administration	у			X														

	Visit	1	2	3	4	5	6	7	8	9	10	11	12	13	14	15	16	17
Procedure Visit Window	Study Day/ Month (Mo.):	Screen N/A	Pre-TX N/A	Day 1 ± 4	Day 14 ± 4	Mo. 1 ± 4	Mo. 2 ± 4	Mo. 3 ± 4	Mo. 4 ± 4	Mo. 5 ± 4	Mo. 6 ± 4	Mo. 7 ± 4	Mo. 8 ±4	Mo. 9 ± 4	Mo. 10 ± 4	Mo. 11 ± 4	Mo. 12/ EOT ± 4	Follow -up/ EOS ²¹ ± 4
V ISIL W INGOV	(Days)	Up to	IN/A	±4	±4	±4	± 4	± 4	± 4	±4	±4	± 4	±4	±4	±4	±4	± 4	±4
Duration		2 mo.	1 week	N/A	N/A	N/A	N/A	N/A	N/A	N/A	N/A	N/A	N/A	N/A	N/A	N/A	N/A	N/A
Calcium and	vitamin D		+						Daily A			-					→	
supplements																		
	dministration			•		•			Daily A	dminist						\longrightarrow	>	
Serum marke metabolism (s-CTX)	s-PINP and			X		X		X			X						X	
Lumbar and tradiographs ⁹	horacic spine	X																
Serum calciu albumin ¹⁰		X		X		X		X			X			X				
24-hour urine (for calcium: creatinine cle	creatinine and			X				X										
Symptom-dri radiologic ass			←							At any	Time							→
Clinical asses	ssment of new		X	X		X		X			X			X			X	
BMD of lum total hip and by DXA ¹³		X						X			X						X	
ADA testing	14			X	X	X		X			X			X			X	X
Assessment of tolerance 15	of local			X	X	X	X	X	X	X	X	X	X	X	X	X	X	
Assessment of adhesion 16				+					Ι	Daily As	sessme	nt —					→	
Subject diary	review ¹⁷			X	X	X	X	X	X	X	X	X	X	X	X	X	X	
Document All concomitant	Es and	At Any Time, Question Subjects at Every Visit							→									
Dispense stud	dy drug			X		X	X	X	X	X	X	X	X	X	X	X		
Sparse PK sa	mpling ¹⁹			X	X	X		X			X			X				

	Visit	1	2	3	4	5	6	7	8	9	10	11	12	13	14	15	16	17
	Study Day/ Month				Day	Mo.	Mo. 12/	Follow -up/										
Procedure	(Mo.):	Screen	Pre-TX	Day 1	14	1	2	3	4	5	6	7	8	9	10	11	EOT	EOS ²¹
Visit Window	v (Days)	N/A	N/A	± 4	± 4	± 4	± 4	± 4	± 4	± 4	± 4	± 4	± 4	± 4	± 4	± 4	± 4	± 4
Duration		Up to 2 mo.	1 week	N/A	N/A	N/A	N/A	N/A	N/A	N/A	N/A	N/A	N/A	N/A	N/A	N/A	N/A	N/A
Collect used swab for abal sMTS ²⁰				X	X	X		X			X			X				

- 1. A complete physical examination includes a review of the following systems: head/neck/thyroid, eyes/ears/nose/throat, respiratory, cardiovascular, lymph nodes, abdomen, skin, musculoskeletal, and neurological. Breast, anorectal, and genital examinations will be performed when medically indicated. After screening, any clinically significant abnormal findings in physical examinations should be reported as AEs.
- 2. Including alcohol and tobacco use assessment.
- 3. Blood pressure, pulse rate, body temperature, and respiration rate are to be recorded predose at each study visit. Only blood pressure, pulse rate, and respiration rate are to be recorded 1 hour after study drug administration at each study visit. All blood pressure assessments will be orthostatic.
- 4. Height is to be measured in the standing position using a medical stadiometer.
- 5. ECGs are to be performed predose and also at 1 hour after study drug administration on Day 1 and Month 12.
- 6. All routine urinalysis will be performed on a sample freshly voided during the visit and sent to a central lab for microscopy if test is positive for micro-organisms via dipstick.
- 7. Screening labs may be analyzed either at a local laboratory or sent to the central laboratory; central laboratory testing must be performed at all other study visits. Blood draws to be done prior to dosing during the treatment period.
- 8. Any subject with a TSH value outside of the normal range may have T3 and free T4 tested, with results within the normal range in order to be enrolled.
- 9. X-ray results will be evaluated by a qualified evaluator at the site, with prevalent fractures assessed using the Genant-semiquantitative scoring method.
- 10. Serum calcium and albumin will be measured predose from the standard chemistry panel on Screening, Day 1, Month 1 and Month 6 and from a separate blood draw predose at Month 3 and Month 9 and at 4 hours postdose at Month 1. Albumin corrected serum calcium will be reported using the serum calcium and albumin results on the following visits: Screening, Day 1, Month 1, Month 3, Month 6 and Month 9.
- 11. A 24-hour urine collection will be collected at Day 1 and Month 3 and will be used for urinary calcium and urinary creatinine measurements. Subjects will discard the 1st void and begin a 24-hour urine collection on the day prior to the study site visit.
- 12. Spine radiographs at screening will be assessed locally. If the subject reports that a fracture has occurred, remind the subject to bring X-rays and any medical reports of the fracture to the next study site visit. Documentation must be obtained on all new fractures that occur during the study. This documentation should be maintained in the source documents.
- 13. Each DXA for a given subject should be performed on the same machine, and if available, preferably by the same technician and will be assessed by a central imaging laboratory. For screening purposes, DXA scans of the lumbar spine, total hip, and femoral neck taken up to 35 days prior to the beginning of the Screening Period may be used to enroll a subject in the study if the BMD T-score criteria in Section 6.2.5 are met.
- 14. Samples for ADA will be drawn prior to treatment on Day 1, Day 14, Month 1, Month 3, Month 6, Month 9, Month 12/EOT, and 1 month following the last dose of study drug. All subjects who remain antibody positive will continue to be followed for ADA testing every 6 months until the result is negative.
- 15. Investigators will perform an assessment of the injection/application site at each study site visit prior to study drug administration, 5 minutes after study drug administration (ie, immediately after patch removal for subjects receiving abaloparatide-sMTS), and 1- hour following study drug administration. Signs of local tolerance will be assessed using a 4-point scale described in Section 6.6.3.1. The subject will maintain a diary of their daily assessment of local tolerance; the application/administration site will be evaluated prior to study drug administration, 5 minutes after study drug administration (ie, immediately after patch removal for subjects receiving abaloparatide-sMTS), and 1 hour following study drug administration daily from Day 1 to the Month 12/EOT visit. Symptoms of local tolerance will be assessed using a 4-point scale described in Section 6.6.3.2.

- 16. Patch adhesion will be assessed by the subject immediately prior to abaloparatide-sMTS patch removal each day during the Treatment Period.
- 17. The subject diary will be reviewed by study personnel at each study visit to ensure subject compliance.
- 18. AEs and SAEs will be recorded on the eCRF starting from the signing of the informed consent until 30 days after the last dose of study drug. All treatment-related AEs will be followed until resolution or stabilization. Any SAEs that occur at any time after completion of the study, which are considered by the Investigator to be related to study treatment, must be reported to the sponsor or its designee.
- 19. Blood samples for measurement of plasma concentrations of abaloparatide will be taken at Day 1, Day 14, Month 1, Month 3, Month 6, and Month 9. One sample per subject per visit will be collected at 1 of the following varying post-injection/application times: 1 hour to 2 hours (Day 1); 30 minutes to 1 hour (Day 14); 3 hours to 4 hours (Month 1); 2 hours to 3 hours (Month 3); 10 minutes to 30 minutes (Month 6) and predose (Month 9). The date and time of injection/patch application and the date and time of PK blood sample collection will be recorded on the CRF.
- 20. Used patches from the study site visits (Day 1, Day 14, Months 1, 3, 6, and 9) including the swab used will be placed in separate vials and shipped to 3M.
- 21. Follow-up/ EOS visit is 1 month (±4 days) after the Month 12/EOT Visit.
 - ADA = Anti-drug antibody; AE=adverse event; BMD=bone mineral density; DXA=dual energy X-ray absorptiometry; eCRF = Electronic case report form; EOS = End of study; EOT = End of treatment; FSH=follicle-stimulating hormone; IRT=Interactive Response Technology; NA=not applicable; PK = Pharmacokinetic; Pre-TX = Pretreatment; PT=prothrombin time; PTH=parathyroid hormone; PTT=partial thromboplastin time; SAEs = Serious adverse events; s-CTX=serum carboxy-terminal cross-linking telopeptide of type 1; sMTS=solid microstructured transdermal system; s-PINP=serum procollagen type 1 N peptide; TSH = Thyroid stimulating hormone.

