6.5. Laboratory Evaluations

6.5.1. Clinical Laboratory Evaluations

Hematology, serum chemistry, and urinalysis will be collected at time points indicated in the Schedule of Assessments and Procedures in Table 1. Screening labs may be analyzed by either a local laboratory or by the central laboratory; all subsequent laboratory tests will be sent to a central laboratory for analysis and testing. A list of study clinical laboratory tests is in Table 2.

Table 2: Clinical Laboratory Tests

Hematology	Serum Chemistry	Urinalysis (dipstick)	Additional Tests
Hemoglobin	Sodium	рН	PTH (1–84)
Hematocrit	Potassium	Glucose	25-hydroxyvitamin D 1,25-dihydroxy vitamin D
WBC count with differential in absolute counts	Chloride	Protein	Estradiol, FSH, TSH, T3, and free T4
RBC count	Inorganic phosphorus	Ketones	Bone-specific alkaline phosphatase ^d
MCV	Albumin	Bilirubin	
MCHC	Total protein	Blood	
MCH	Glucose	Urobilinogen	
Platelet count	BUN	Specific gravity	
Coagulation (PT and PTT)	Creatinine	Nitrite	
	Uric acid	Leukocytes	
	AST		
	ALT		
	GGT		
	СРК		
	Alkaline phosphatase		
	Total bilirubin		
	LDH		
	Total cholesterol		
	Triglycerides		
	Total calcium		

ALT = Alanine aminotransferase; AST = Aspartate aminotransferase; BUN = Blood urea nitrogen; CPK = Creatine phosphokinase; FSH = Follicle-stimulating hormone; GGT = Gamma-glutamyltranspeptidase; LDH = Lactate dehydrogenase; MCH = Mean corpuscular hemoglobin; MCHC = Mean corpuscular hemoglobin concentration; MCV = Mean corpuscular volume; PT = Prothombin time; PTH = Parathyroid hormone; PTT = Partial thromboplastin time; RBC = Red blood cell; TSH = Thyroid stimulating hormone; WBC = White blood cell.

In the event of medically significant, unexplained, or abnormal clinical laboratory test values, the test(s) should be repeated and followed up until the results have returned to within the normal range or an adequate explanation for the abnormality is found. Clinically significant changes in laboratory tests that occur during the course of the study are to be reported as AEs.

The clinical laboratory will clearly mark all laboratory test values that are outside the normal range and the Investigator will indicate the clinical relevance of these out of range values.

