#### **4.6.5.      Laboratory Data**

Clinical laboratory values will be provided in conventional units and in standard international (SI) units by the central laboratory, unless otherwise specified.

In this study, local labs were allowed for screening. In addition, the original central lab was [REDACTED] Midway through the study, [REDACTED] was replaced with Medpace. Normal values of laboratory parameters in this study were provided by different local and central laboratories with inconsistent units and normal ranges. Thus, all numerical values will be converted to SI units and normalized to a standard set of reference/normal ranges as described by Chuang-Stein (1992 and 2001). The normalization process will be performed separately for each of the laboratory parameters as described in [Appendix D](#), using the Medpace normal ranges as the reference ranges.

Summaries of laboratory data will be presented using normalized laboratory values. Summaries using descriptive statistics by treatment group and study visit will be presented based on the SI units, including absolute results and changes from baseline. This includes serum chemistry, hematology, coagulation, urinalysis (for quantitative urinalysis assays), hormones and Vitamin D. In the event of repeat assessments, the last non-missing value per study day/time will be used in the summary statistics. Results from unscheduled visits will not be included in the descriptive summary tables.

Tables for the shift of laboratory data from baseline to the worst post-baseline value and from baseline to Month 12 (Visit 16) will be presented by treatment group. Results for serum chemistry, hematology, coagulation, and urinalysis will be presented by category (above normal limit, within normal limit, below normal limit). For shift tables from baseline to worst post-baseline value, and for baseline to Month 12, percentages will only be calculated based on the number of subjects with valid data for baseline and post-baseline; subjects who are missing either assessment will not be included in the percentage calculation (numerator or denominator). Results from repeat/unscheduled visits will be included in the shift analyses, as applicable.

Summaries of all laboratory parameters will also be presented by region (North America and Europe).

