Any laboratory parameter value that is provided as “*< numeric value*” or “*> numeric value*” will be imputed as the *numeric value* in all summary tables and analyses, but will be shown with the actual result in the listings.

All laboratory data, including repeat and unscheduled assessments, will be presented in data listings, with indication of higher or lower than the associated normal range of each laboratory test, where applicable. Lab listings will show values in original results (in conventional units), results in SI units, and normalized values.

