#### **4.6.5.1. Potentially Clinically Significant Laboratory Values**

Criteria for determining values of laboratory tests that are considered potentially clinically significant (PCS) are listed in [Appendix C](#) of this SAP. The number (%) of subjects with post-baseline PCS values who did not have PCS values at baseline will be presented for each laboratory parameter with PCS criteria. Results from unscheduled visits will be included in identification of subjects with post-baseline PCS values, as applicable. For the calculation of the percentages of subjects, the denominator will be based on the number of subjects who had no PCS values at baseline and had at least one post-baseline assessment for the specific laboratory parameter of interest. The numerator will be based on the number of subjects from the denominator who had at least one PCS value post-baseline for the specific laboratory parameter of interest.

A listing of subjects with any PCS laboratory values will be provided.

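### The PCS limit for urine blood needs a red-cell count that the scheduled dipstick cannot give, so that row will undercount haematuria and its denominator is unclear

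*Protocol*

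**What the plan says.** Protocol Table 1 schedules dipstick urinalysis at Screening, Day 1 and Months 1, 6 and 12. Protocol Table 2 (Section 6.5.1) lists ten dipstick items, including blood, nitrite and leukocytes. It lists no microscopic red-cell count.

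Table 1 footnote 6 says that a routine sample is "sent to a central lab for microscopy if test is positive for micro-organisms via dipstick". The SAP repeats this footnote in its own Table 1. Section 6.5.1 adds that, after screening, "all subsequent laboratory tests will be sent to a central laboratory for analysis and testing", but says nothing there about microscopy.

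SAP Appendix C gives three urine limits. Glucose and protein are each flagged at dipstick grade 2+. Blood is flagged at >50 rbc/hpf in both the conventional-unit and SI-unit columns, with no dipstick alternative.

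SAP 4.6.5.1 describes the table these limits feed: "The number (%) of subjects with post-baseline PCS values who did not have PCS values at baseline will be presented" for each parameter that has a criterion. For the percentages, "the denominator will be based on the number of subjects who had no PCS values at baseline and had at least one post-baseline assessment" of the parameter concerned. Results from unscheduled visits count towards identifying PCS values.

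**The concern.** The criterion and the measurement are on different scales. A dipstick does not yield red cells per high-power field, and the one written route to that unit depends on a different finding, micro-organisms. The glucose and protein lines do not have this problem, so the gap is specific to blood.

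Urine safety has some relevance here. The protocol lists hypercalciuria among the most common adverse reactions to abaloparatide-SC (Section 1.1.2.2.1), excludes women with kidney or urinary stones in the past 5 years (exclusion criterion 11), and has a hypercalciuria algorithm (Section 4.7.2). A nearly empty PCS row for urine blood could be read as evidence that haematuria was rare, when the plan gave most such findings no route into the row.

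**Working it through.** No figure in the plan bears on this point, so there is none to reproduce. The check sets the documents side by side.

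**Step 1. Can the scheduled dipstick decide each urine criterion?**

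| Urine parameter | Dipstick item (Protocol Table 2) | PCS limit (SAP Appendix C) | Dipstick alone sufficient? |
|---|---|---|---|
| Glucose | Yes | Grade 2+ | Yes |
| Protein | Yes | Grade 2+ | Yes |
| Blood | Yes | >50 rbc/hpf | No |

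**Step 2. When is a red-cell count planned? (Table 1 footnote 6)**

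| Dipstick blood | Dipstick micro-organisms | Microscopy planned | Blood criterion can be assessed |
|---|---|---|---|
| Positive | Positive | Yes | Yes |
| Positive | Negative | No | No |
| Negative | Positive | Yes | Yes |
| Negative | Negative | No | No |

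The second line is the gap. The trigger is itself loosely defined, because Table 2 has no micro-organism item. Nitrite or leukocytes are presumably the proxies (assumption).

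**Step 3. What does this do to the PCS percentage?** Take women with at least one post-baseline dipstick and no PCS value at baseline, and write:

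- *N* for their number;
- *m* for those with at least one post-baseline microscopy;
- *x* for those whose urine would exceed the limit if it were counted;
- *x*ₘ for those whose exceedance fell on a sample that went to microscopy, so *x*ₘ ≤ *x*.

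The quantity wanted is *x*/*N*. The reported numerator is *x*ₘ, so the shortfall is *x* − *x*ₘ. SAP 4.6.5.1 allows two denominators:

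- **Only microscopy counts as an assessment of blood.** The rate is *x*ₘ/*m*. The group *m* is selected mainly by signs of infection, so this rate can lie on either side of *x*/*N* and does not describe the treated population.
- **The dipstick counts as an assessment of blood.** The rate is *x*ₘ/*N* ≤ *x*/*N*. Women without microscopy are in the denominator but cannot enter the numerator, which pulls the rate towards zero.

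The SAP does not say which reading applies. The baseline condition has the same gap: without baseline microscopy, a woman's baseline PCS status for blood is unknown.

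**Step 4. Size.** The documents give none of *m*, *x* or *x*ₘ, and no rate of dipstick-positive blood or of microscopy. The direction of the error in the count is clear; its size cannot be computed.

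**The case against.** The strongest reply is that other outputs can show haematuria, and this is largely right.

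- SAP 4.6.5 plans urinalysis shift tables by treatment group, from baseline to the worst post-baseline value and to Month 12, with unscheduled results included. Protocol 8.4.4 plans the same kind of classification.
- Laboratory listings show all data, "with indication of higher or lower than the associated normal range of each laboratory test, where applicable".
- Protocol 6.5.1 requires significant or unexplained abnormal values to be repeated and followed up, and states that "Clinically significant changes in laboratory tests that occur during the course of the study are to be reported as AEs". Treatment-emergent events are tabulated by system organ class and preferred term.

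A reader might infer that haematuria without infection can never be counted in this trial. The documents do not support that. Footnote 6 says microscopy is done if the dipstick shows micro-organisms; it does not forbid microscopy for another reason. A red-cell count from an unscheduled visit can enter the PCS row.

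A reader might also infer that the row is limited to women with a suspected urinary infection. That is only one reading. Blood is a dipstick item, so a dipstick may count as an assessment of that parameter. Nor can the gap be sized by guessing a microscopy rate: the result would only be one minus the guess, and would measure samples without microscopy, not missed events.

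Relevance is also limited. Haematuria is neither an endpoint nor a listed AESI, and hypercalciuria has its own 24-hour urine analysis.

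What remains is the row itself. Shift tables separate only above, within and below normal, so they cannot isolate a marked result. Listings give no rate by arm. AE reporting rests on investigator judgement in an open-label trial. The repeat-testing rule does not call for microscopy. None of these repairs the PCS percentage.

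**Conclusion.** The point holds for one row of one table. From scheduled samples, the PCS count for urine blood will miss any exceedance not accompanied by a micro-organism-positive dipstick, and the denominator is ambiguous, with neither reading giving a sound rate. This assumes that the sites follow footnote 6 as written, and that no red-cell count is routinely reported outside it; the separate Laboratory Manual was not available to check.

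The size of the undercount is unknown. The rule is the same in both arms, so nothing in the documents shows that it favours one treatment. The primary analysis and the sample size are unaffected, and AE reporting stands. This is a safety-reporting defect, worth correcting because the row could otherwise be read as reassurance it cannot give.

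**What to change.** In SAP Appendix C, add a PCS criterion for urine blood based on the dipstick result, in the same form as the glucose and protein lines. Set it on the scale that the laboratory actually reports, since Protocol Table 2 gives no reporting scale for blood. SAP 4.6.5 records a change of central laboratory during the study, so confirm that the scale is common to both or state how results are mapped.

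In SAP 4.6.5.1, state that for urine blood the baseline status, numerator and denominator all use dipstick results, with the denominator drawn from every subject who has a post-baseline dipstick. Report >50 rbc/hpf separately, for samples that had microscopy, giving the number of samples examined by arm.

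The cost is SAP wording and programming for one row. Dipstick blood is already scheduled, so no new sample or visit is needed. The downside is that this row departs from the published grading scale cited in Appendix C and is less specific than a red-cell count, so the chosen grade needs a sentence of justification. If the change follows SAP finalisation and is judged significant, SAP Section 1 calls for it to be identified in Section 9.8 of the clinical study report.
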